## 6.0 Simulation Scenarios

In order to characterize the performance of the trial design, we simulated the trial considering different scenarios for the proportion of patients achieving a response at 12 months and the longitudinal behavior of the primary endpoint.

## 6.1 Response Scenarios

We specify the scenarios for achieving a response at 12 months in terms of the mean and standard deviation of the PBLAC score at 12 months. Because we model the log of the PBLAC score in the longitudinal modeling, we also specify the scenarios for achieving a response at 12 months on the log scale. We consider 4 different standard deviations (SDs) for the log of the PBLAC score and then determine the mean that achieves a specific proportion of patients who would be considered responders. We consider SDs for PBLAC on the log scale of 1, 0.95, 0.75, and 0.5. Table 6.1 shows the means and SD on both the log PBLAC scale and PBLAC score scale that correspond to the indicated proportion of patients achieving a response.

**Table 6.1 Response Scenarios: Mean and SD of the log PBLAC Score and Corresponding Proportion Responding**

	Proportion Responding	Log PBLAC Scale				PBLAC Scale			
		SD = 1	SD = 0.95	SD = 0.75	SD = 0.5	Mean	Mean (SD)	Mean (SD)	Mean (SD)
		Mean	Mean	Mean	Mean	Mean (SD)	Mean (SD)	Mean (SD)	Mean (SD)
1	60%	4.06	4.076	4.13	4.19	96 (126)	93 (112)	82 (72)	75 (40)
2	66%	3.905	3.925	4.009	4.111	82 (107)	80 (96)	73 (63)	69 (37)
3	70%	3.79	3.82	3.93	4.05	73 (94)	72 (87)	67 (59)	65 (35)
4	75%	3.64	3.676	3.81	3.98	63 (81)	62 (75)	60 (51)	61 (32)
5	80%	3.477	3.518	3.685	3.895	53 (70)	53 (64)	53 (46)	56 (30)
6	85%	3.281	3.333	3.539	3.799	44 (57)	44 (53)	46 (40)	51 (27)
7	90%	3.036	3.1	3.353	3.677	34 (45)	35 (42)	38 (33)	45 (24)

## 6.2 Longitudinal Profiles

We specify the longitudinal behavior of the PBLAC score by specifying the mean and SD of the log PBLAC score at each earlier visit as well as the correlation between the log PBLAC scores from visit to visit.

### 6.2.1 Response Fraction

We specify the mean and SD of the log PBLAC score at each earlier visit in terms of a multiplier on the final 12 month log PBLAC score. For example a multiplier of 1 would indicate the same mean PBLAC at an earlier visit as compared to the mean 12-month value and a multiplier of 2 would indicate a mean PBLAC score twice the mean 12-month value. In general we consider scenarios where baseline PBLAC scores are higher at baseline and where much of the reduction in the PBLAC score is achieved by the 3-month visit. For the variance of the log PBLAC at each visit, we consider scenarios where either there is a constant variance for the log PBLAC at each visit, or that the earlier values will have larger variability.

The table below shows the different simulation scenarios for the behavior of the mean and the variance of the log PBLAC at each visit.

Table 6.2.1: Multipliers for the Mean and Variance of the log PBLAC at Each Visit			
	Baseline	3 Months	6 Months
Scenarios for Mean			
1. High Baseline and Early Response	1.48	1.07	0.96
2. Higher Baseline and Early Response	1.6	1.2	0.8
3. Higher Baseline and Late Response	1.6	1.2	1.05
Scenarios for Variance	1.5	1.12	1
1. Higher Variance Early	2	2	1.5
2. High Variance Early	1.5	1.12	1
3. Constant Variance	1	1	1

### 6.2.2 Visit-to-Visit Correlation

The values of the primary endpoint are correlated within each patient from visit to visit. The table below shows the correlations we assume for the log PBLAC score within a patient between each visit.

Table 6.2.2: Correlation Scenarios		
	Weaker Correlation	Stronger Correlation
Baseline to 3 Months	0.1	0.35
3 Months to 6 Months	0.8	0.76
6 Months to 12 Months	0.3	0.6

### 6.3 Accrual and Dropout

We consider an accrual scenario in which accrual ramps up linearly for 12 weeks to a peak accrual rate of 11 patients per week. All patients will have been enrolled between 6 and 8 months of total trial time. We simulate no drop-outs, 5%, 10%, and 15% drop-out. In the primary analysis, any patient who does not have a 12-month value will be considered a failure.

## 7.0 Operating Characteristics

Table 7.1 shows the operating characteristics of the trial design. Results are based on at least 5000 simulations for each scenario. We show the probability of achieving early success and the probability the trial does not achieve an early success but claims success at trial completion (Probability of late success). The total probability of success is the sum of achieving a success, either early or late. All patients are expected to be treated at the time the first interim analysis occurs so the trial's mean sample size is 242 patients.

The operating characteristics presented here are based on the response scenarios in which the SD of the log PBLAC is 0.95. The longitudinal profile of the virtual patients is based on scenarios with a high baseline score and more patients achieving a response at 6 months than at 12 months (Table 6.2.1 mean scenario 1), a high variance for the PBLAC at earlier timepoints (Table 6.6.1 variance scenario 2), and the stronger visit-to-visit correlation. Based on patient-level data from a previous trial of the Cerene device, this is the expected profile of patients who will be enrolled and treated in this trial. We show results across the various assumptions for the proportion of patients dropping-out before 12 months. Operating characteristics based on other simulation scenarios are shown in the appendix.

**Table 7.1: Operating Characteristics**

Response Among 12-Month Completers	ITT Response	Pr (Early Success)	Pr (Late Success)	Total Pr (Success)
No Drop-Outs				
60%	60.0%	0	0.000	0.000
**66%	66.0%	0.000	0.025	0.025
70%	70.0%	0.015	0.230	0.245
75%	75.0%	0.295	0.571	0.866
80%	80.0%	0.900	0.098	0.998
85%	85.0%	0.999	0.001	1.000
90%	90.0%	1.000	0.000	1.000
5% Drop-Out				
60%	57.0%	0	0	0
66%	62.7%	0	0.001	0.001
70%	66.5%	0.001	0.038	0.039
75%	71.3%	0.044	0.357	0.401
80%	76.0%	0.483	0.441	0.924
85%	80.8%	0.966	0.034	0.999
90%	85.5%	0.999	0.000	0.999
10% Drop-Out				
60%	54.0%	0	0	0
66%	59.4%	0	0	0
70%	63.0%	0	0.001	0.001
75%	67.5%	0.003	0.067	0.070
80%	72.0%	0.105	0.391	0.497
85%	76.5%	0.643	0.303	0.947
90%	81.0%	0.988	0.012	1.000

\*\*10,000 simulations

If the response rate is less than the OPC, 60%, there is a 0% probability of trial success. Under the null hypothesis, that response rate is the same as the OPC, 66%, this trial will not achieve early success, but will achieve success with complete follow-up on all patients with 2.5% probability. This is the simulated one-sided Type I error rate in this scenario. Given that the final evaluation of trial success is based on the dichotomous responses endpoint with complete data among all enroll patients, and that the longitudinal model has no role in the primary efficacy analysis, the overall Type I error rate does not depend on the mean or standard deviation of the PBLAC score, accrual rates, or longitudinal profile assumptions. The simulated Type I error rate here is shown to be controlled to < 2.5% with a critical value of

97.9%, but given there is a single final evaluation of trial success based on complete data, a critical value of 97.5% could also be considered appropriate.

Under an alternative hypothesis, that the response rate is 75%, this trial will stop early for success with approximately 30% probability. The total probability of trial success in this scenario is 87%. This is the power of the trial in this scenario. As the drop-out rate increases, the observed response rate at 12 month decreases and patients who are missing their 12 month observation are counted as non-responders. Correspondingly, the power of the trial decreases. If 5% of patients drop-out and there is an 80% response rate among completers at 12 months, the response rate in the ITT population will be 76% and there is a 92.4% probability of trial success. If 10% of patients drop-out and there is an 85% response rate among completers at 12 months, the response rate in the ITT population will be 76.5% and there is a 94.7% probability of trial success.

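### The final rule amounts to at least 175 of 242 responders, with exact Type I error 2.1% and power 85.0%; the plan states simulated figures of 2.5% and 87%

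*SAP*

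**What the plan says.** SAP 2.2 puts a normal prior with mean 0 and SD 2 on the log-odds of response, counts a missing 12-month value as non-response, and gives the longitudinal model no part in the final primary analysis. SAP 4.0 declares success if the posterior probability that the response rate exceeds 66% is above 0.979. It applies this test once all 242 patients have had the chance to reach 12 months, even after an early declaration. Protocol 4.1.6 says the same about the final evaluation.

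SAP 7.0 then reports simulated operating characteristics. At 66% the trial "will achieve success with complete follow-up on all patients with 2.5% probability". At 75% with no drop-out, "The total probability of trial success in this scenario is 87%. This is the power of the trial in this scenario". Protocol 4.1.8.5 repeats both figures. SAP 7.0 also explains how the total is formed: "The total probability of success is the sum of achieving a success, either early or late". Of the 75% scenario it says that "this trial will stop early for success with approximately 30% probability".

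Protocol 4.1.3 promises at least 85% power at 75% and an overall Type I error below 2.5%. Neither document states a pass mark as a number of responders.

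**The concern.** With one arm, a fixed denominator of 242, missing values counted as failures and no modelling at the end, the final test depends only on the number of responders. Its error rate and power can therefore be calculated exactly. The printed simulated figures should agree with that calculation within Monte Carlo error, apart from trials that declare early success and then miss at the end.

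At stake are the two headline operating characteristics of a pivotal study. A reader takes 2.5% and 87% to describe the rule that decides the trial. If they do not, the apparent two-point cushion over the promised 85% power is not there. The pass mark, which is the most useful fact about the rule, also stays unstated.

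**Working it through.** **Inputs.** N = 242, threshold 0.979 and performance goal 0.66 (SAP 4.0); prior θ ~ N(0, 2²) and missing = non-response (SAP 2.2); alternative 0.75 (SAP 7.0); 10,000 runs at 66% and at least 5,000 elsewhere (SAP 7.0 and the note to Table 7.1).

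**The plan's own figures.** Table 7.1, no drop-out: 0.000 early + 0.025 late = 0.025 at 66%; 0.295 + 0.571 = 0.866 at 75%, quoted as 87%. The table adds up, so the question is whether these totals describe the final rule.

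**Pass mark.** For x responders the posterior density of θ is proportional to exp(xθ) / (1 + exp(θ))^242 × exp(−θ²/8). Integrating over θ > log(0.66/0.34), and taking P(X ≥ x) for X ~ Binomial(242, p):

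| Responders | Pr(π > 0.66) | Passes 0.979? | Exact Type I error (p = 0.66) | Exact power (p = 0.75) |
|---|---|---|---|---|
| 174 | 0.97495 | no | 2.93% | 88.16% |
| 175 | 0.98211 | yes | 2.11% | 85.05% |
| 176 | 0.98746 | yes | 1.49% | 81.42% |

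Each row's error and power are those of a rule that passes from that count upward. The plan's rule is the 175 row. No neighbouring cutoff gives the printed pair.

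**Type I gap against Monte Carlo error.**
- SE = √(0.0211 × 0.9789 / 10,000) = 0.0014, so the gap is (0.025 − 0.0211) / 0.0014 = 2.7 SE.
- The Table 6.1 mean for the 66% scenario (3.925, SD 0.95) implies a true rate of 66.02%, at which the exact error is 2.15%. The gap becomes 2.4 SE.
- If the unrounded simulated value was also as low as 0.0245, the gap is 2.0 SE.
- Early declarations add nothing, because early success at 66% is 0.000.

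**Power gap.**
- SE = √(0.8505 × 0.1495 / 5,000) = 0.0050, so the gap is (0.866 − 0.8505) / 0.0050 = 3.1 SE. More than 5,000 runs would make it larger in SE units.
- The Table 6.1 mean (3.676) implies 75.02%, with exact power 85.25%: 2.7 SE.
- Protocol 4.1.8.5 puts the chance that an early success is not confirmed below 1%. Read as a share of early declarations, this adds at most 0.01 × 0.295 = 0.3 point: 85.55%, 2.1 SE.
- Read as a share of all trials, it adds up to 1 point: 86.25%, 0.7 SE.

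**Margin.** 85.05% − 85% = 0.05 point. Exact power falls below 85% once the intention-to-treat response rate is below 74.99%.

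**Other rows, printed total / exact final-only.** The drop-out rows assume that each patient drops out independently, so the response rate is the completer rate × (1 − drop-out).

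| Drop-out | Completer rate | Printed total | Exact final-only |
|---|---|---|---|
| none | 66% | 0.025 | 0.021 |
| none | 70% | 0.245 | 0.239 |
| none | 75% | 0.866 | 0.850 |
| 5% | 70% | 0.039 | 0.031 |
| 5% | 75% | 0.401 | 0.388 |
| 5% | 80% | 0.924 | 0.920 |
| 10% | 75% | 0.070 | 0.062 |
| 10% | 80% | 0.497 | 0.489 |
| 10% | 85% | 0.947 | 0.944 |

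All nine printed values are higher, four of them by more than 2 SE (66% and 75% without drop-out; 5%/70%; 10%/75%).

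**The case against.** The strongest reply is that no promise is broken. Protocol 4.1.3 commits to at least 85% power and an error below 2.5%, and the exact values meet both. The 2.5% is openly labelled as simulated, and SAP 7.0 defines the total as early or late. This stands, and it limits the point to reporting.

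It is also fair to say that no faulty step can be identified. On the broader reading of the below-1% statement the power gap is within chance, and five of the nine rows lie within 2 SE. SAP 6.3 lists drop-out levels ("We simulate no drop-outs, 5%, 10%, and 15% drop-out") but no mechanism. With a fixed number of drop-outs the 10%/85% row would be 0.967 to 0.977, above the printed 0.947, so the pattern in the drop-out rows rests on an assumption. Noise in a simulated posterior is possible, but the SAP does not describe it. None of this turns 87% into the power of the final rule, and the Type I gap remains at 2.0 SE with every rounding allowance made.

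Two further complaints might be inferred and should not be pressed. The SAP states that "The simulated Type I error rate here is shown to be controlled to < 2.5"% beside a printed 0.025, but a value just under 0.025 would print that way, and the exact 2.1% bears the statement out. The sentence that "the overall Type I error rate does not depend on the mean or standard deviation of the PBLAC score" opens by tying itself to the final evaluation on complete data, for which it is correct. The remark that "a critical value of 97.5% could also be considered appropriate" changes nothing at 242 patients: 174 responders give 0.97495, so the pass mark is 175 at either threshold.

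**Conclusion.** The point holds as a reporting error. The rule that decides the trial is at least 175 of 242 responders, with exact Type I error 2.1% and power 85.0%, against the stated 2.5% and 87%. The pass mark and the no-drop-out values follow from SAP 2.2 and 4.0 with no further assumption except a common response rate across independent patients. The cause of the higher simulated values cannot be settled from the documents.

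A reader might infer that Type I error is inflated or that the study is underpowered. The documents support neither: the exact error is lower than the stated one, and the exact power still meets the promised 85%. What changes is the cushion, which is 0.05 point rather than about two. Separately, saying that the trial stops early conflicts with SAP 4.0 and Protocol 4.1.6, under which it continues to a final evaluation. Protocol 4.1.8.5 already speaks of declaring early success.

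**What to change.** 1. In Protocol 4.1.8.5 and SAP 7.0, add: *The final analysis succeeds if at least 175 of 242 patients are responders, with missing 12-month values counted as non-response. Exact one-sided Type I error is 2.1% at 66%, and exact power is 85.0% at 75%.*
2. Keep the simulated columns of Table 7.1, and label the 87%, 92.4% and 94.7% in the text below it as simulated early-or-late totals. Label the 87% in Protocol 4.1.8.5 in the same way.
3. Optionally, add the exact final-only values tabulated above, stating that the drop-out rows assume independent drop-out.
4. In SAP 7.0, change the wording about stopping early to declaring early success.

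The cost is a few sentences and, if wanted, one table column. The stated power falls from 87% to 85.0%. Sample size, threshold and analyses are unchanged, and no new simulation is needed.
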